9.3.5 Early Terminations and Protocol Deviations

The following rules and conventions will be used for patients who terminate from the study early or are dropped from the study because of protocol deviations.

If a patient terminates from the study early, all efforts will be made to complete Visit 7 study procedures.

Any patient who either requests to be dropped from the study because of lack of therapeutic efficacy or is dropped by the Investigator for lack of therapeutic efficacy will automatically be considered a "clinical failure" irrelevant of their target toenail assessment score at the termination visit.

Any patient who uses any protocol restricted medication specifically for the treatment of their infection will be discontinued from further participation in the study and automatically be considered a "clinical failure" irrelevant of their target toenail assessment score at the last visit.

Any patient who uses any protocol restricted medication NOT specifically for the treatment of their onychomycosis will be discontinued from further participation in the study. The patient will be considered a "clinical cure" or "clinical failure" based on the target toenail assessments at the termination visit.

Any patient who is dropped for any other reason, other than those covered above, had a positive baseline culture and makes at least one post-baseline visit where clinical assessments for target toenail are performed and/or a KOH and/or mycological culture result is obtained, will be

A Randomized, Placebo-Controlled, Double-Blind, Parallel-Group, Multi-Site Phase 2b Clinical Study to Assess the Efficacy, Safety and Tolerability of 8-Week Regimens of Novexatin[®], 10% Topical Solution (Taro Pharmaceuticals, USA, Inc.) in Patients with Mild to Moderate Onychomycosis

included in the ITT. Examples would include: failure to use the study products as required by the protocol (see section 9.4.5), patient withdraws consent for continued participation, patient fails to make study visits on a timely basis.

9.3.6 Clinical Study Termination

The clinical study may be terminated if:

- The Sponsor considers the applied dose of the study product to be no longer relevant
- The Sponsor decides to terminate the clinical study, in particular because data not known before become available and raise concern about the safety of the patients so that continuation of the clinical study would pose potential risks to the patients

Termination of the clinical study, for any reason, must be mutually agreed upon by the Principal Investigator and the Sponsor, and must be documented. However, clinical study results will be reported according to the requirements outlined in this protocol as far as applicable.

9.4 Treatments

9.4.1 Treatments Administration

Patients will be provided with verbal and written instructions on how to dose. Patients are to begin dosing on Day 1 in the office with a clinic staff member observing.

The following treatments will be assessed in this study:

- **Treatment Group A:** Test treatment for Days 1 – 56 and Placebo treatment for Days 281 – 336
- **Treatment Group B:** Test treatment for Days 1 – 56 and Days 281 – 336
- **Treatment Group C:** Placebo treatment for Days 1 – 56 and Days 281 – 336

Study treatment is to be administered by the patient once daily, preferably in the morning after cleaning the affected area with non-medicated soap and patting dry with soft towel. The nails should be completely dry before applying product. A single dose is approximately 30 µl of topical solution. The material will be applied to toenails with a brush that will provide a maximum volume of up to 50 µl after a single fill. A volume of 30 µl to 50 µl of the solution will cover a single nail and nearby skin, depending on the size of the nail. Daily applications of a 10% concentration will provide between 3 - 5 mg of Novexatin per nail. The date and time of each dose must be recorded in the dosing section of the patient diary.

Details of dose administration

The study products will be administered at home by the patients according to the procedure below. The first dose will be applied by the patient in the clinic at Visit 2, with a clinic staff member observing.

A Randomized, Placebo-Controlled, Double-Blind, Parallel-Group, Multi-Site Phase 2b Clinical Study to Assess the Efficacy, Safety and Tolerability of 8-Week Regimens of Novexatin®, 10% Topical Solution (Taro Pharmaceuticals, USA, Inc.) in Patients with Mild to Moderate Onychomycosis

- Apply the study product at approximately the same time each day, leaving sufficient time post-application for the solution to dry on the nail (the solution will dry in approximately the same time as required for cosmetic nail polish and will be dry to the touch)
- Using the supplied brush, spread a liberal amount of the study product evenly across all toenails on feet with affected toenails and adjacent skin of the toes, working from the outside of the nail inwards to ensure the nail edges have made contact with the solution

9.4.2 Identity of Investigational Product

The following products will be used in this study:

Test: Novexatin® 10% Topical Solution (Taro Pharmaceuticals, USA)

Placebo: Placebo (Vehicle) Topical Solution (Taro Pharmaceuticals, USA)

The active ingredient in Novexatin® study products is presented as a 100 mg/ml (10%) solution of net peptide of Cyclo [7xArg] for topical application to the surface of the toenail. All study medication will be supplied in capped high-density glass amber bottles with a nylon brush.

All randomized study product will be blinded and packaged in blinded sealed boxes or bags. Each bottle will be identified only by a label bearing the Sponsor name, protocol number, randomization number, treatment duration and a statement that the study product is for Investigational Use Only. The study staff will dispense the study product bottle only to those patients identified by the Investigator. The study staff will instruct the patients on the use and return of study product.

Individual bottles of study product for Visit 2 (randomization) will be packaged in blocks. One block will consist of three boxes of study product containing 2 bottles (#1 & 2) according to the randomization code. Bottles # 3 & 4 will be provided for all active patients at sites before Visit 5. The study product will be provided in three configurations:

- A. bottles #1 & 2 – Test and bottles #3 & 4 – Placebo
- B. bottles #1 & 2 – Test and bottles #3 & 4 – Test
- C. bottles #1 & 2 – Placebo and bottles #3 & 4 – Placebo

The study product will be shipped to each Investigator's site from a centralized pharmacy for the initial shipments. Site to site study product distribution and shipping is allowable in cases approved by the sponsor. The Principal Investigator at each site is responsible for ensuring that all study products are stored in a locked, secure location, with access limited to the Investigator and his/her designee(s). An accurate inventory of the study product will be maintained in accordance with federal regulations.

Once the site has been notified that they may do so, all unused study product and empty or partially used bottles of study product may be returned to the Sponsor or designee.

Storage Conditions:

A Randomized, Placebo-Controlled, Double-Blind, Parallel-Group, Multi-Site Phase 2b Clinical Study to Assess the Efficacy, Safety and Tolerability of 8-Week Regimens of Novexatin®, 10% Topical Solution (Taro Pharmaceuticals, USA, Inc.) in Patients with Mild to Moderate Onychomycosis

Study product will be stored at controlled room temperature, away from direct sunlight exposure, at 25°C (77°F), with excursions permitted between 15°C and 30°C (59°F and 86°F). The Principal Investigator at each site is responsible for ensuring that all study products are stored in a locked, secure location, with access limited to the Investigator and his/her designee(s).

9.4.3 Method of Assigning Patients to Treatment Groups

9.4.3.1 Enrollment

At Visit 2 eligible patients will be randomized to the study and assigned enrollment randomization number. Randomization numbers will consist of a 2-digit site number and 4-digit randomization number. The 4-digit randomization numbers will be assigned in ascending order beginning with the lowest number at each study site.

9.4.3.2 Randomization

The study product will be packaged and blinded by an independent clinical packaging company. The randomization will be generated in blocks of 3, containing the study products in three configurations:

- A. bottles #1 & 2 – Test and bottles #3 & 4 – Placebo
- B. bottles #1 & 2 – Test and bottles #3 & 4 – Test
- C. bottles #1 & 2 – Placebo and bottles #3 & 4 – Placebo.

Three patients worth of study product bottles 1 & 2 will be packed into a larger box. This larger box will be designated “one block” of study product. The study product bottles 1 & 2 will be blinded, packaged and delivered to the study site in blocks at the beginning of the enrollment. Bottles 3 & 4 will be delivered to the study site before Visit 5 (2nd treatment start).

At each Visit 2 and Visit 5 each patient will receive two 5 ml bottles of study product according to the randomization code. Patients will be randomized to a treatment regimen in a blinded fashion by assigning randomization numbers in ascending sequential order starting with the lowest available randomization number at each site. All patients randomized will be identified by initials, date of birth, and a unique six-digit patient number. The first two-digits will identify the Investigator site where the patient was enrolled and the last four will correspond with the randomization number of study product bottle assigned to the patient. A perforated or two-part label will be attached to each of the small sized boxes of study product supplies. Both pieces of the label will include the following information: Protocol number, randomization number, space for patient’s initials, statement that the study product is for investigational use only, space for dispensing date and the Sponsor’s name. In addition all patients will be provided with written instructions on how to use the study product. One part of the label shall remain attached to the box. The other part will be removed prior to dispensing and attached to the study product log.

A Randomized, Placebo-Controlled, Double-Blind, Parallel-Group, Multi-Site Phase 2b Clinical Study to Assess the Efficacy, Safety and Tolerability of 8-Week Regimens of Novexatin®, 10% Topical Solution (Taro Pharmaceuticals, USA, Inc.) in Patients with Mild to Moderate Onychomycosis

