9.0 INVESTIGATIONAL PLAN

9.1 Study Design and Plan Description

This randomized, placebo-controlled, double-blind, parallel-group, multi-site study is designed to evaluate and compare the efficacy and safety of two dosing regimens of Novexatin® 10% topical solution (Taro Pharmaceuticals USA) for the treatment of mild to moderate distal subungual onychomycosis of the target toenail. Additionally the active formulation in these regimens will be assessed for superiority to a placebo topical solution.

Up to 180 eligible patients with distal subungual onychomycosis who meet all the inclusion criteria and none of the exclusion criteria will be enrolled into the study at Visit 1. Patients must be at least 18 years of age, in overall good health. They should have a current diagnosis of distal subungual onychomycosis of mild-moderate severity. Before any study-specific procedures are performed all patients will read and sign the IRB-approved informed consent form.

At least 60 qualified patients in each treatment group will receive randomized and blinded study product. The randomization scheme will be 1:1:1 (Active Treatment A: Active Treatment B: Placebo C). The study products are:

Test: Novexatin® 10% Topical Solution (Taro Pharmaceuticals, USA)

Placebo: Placebo (Vehicle) Topical Solution (Taro Pharmaceuticals, USA)

Patients will be assigned to one of the three treatment groups as outlined below and described in Section 9.4 of this protocol.

Treatment Group A: Test treatment for Days 1 – 56 and Placebo treatment for Days 281 – 336

Treatment Group B: Test treatment for Days 1 – 56 and Days 281 – 336

Treatment Group C: Placebo treatment for Days 1 – 56 and Days 281 – 336

Treatment and study durations will be as follows:

Study Duration: 365 days (52 weeks)

A Randomized, Placebo-Controlled, Double-Blind, Parallel-Group, Multi-Site Phase 2b Clinical Study to Assess the Efficacy, Safety and Tolerability of 8-Week Regimens of Novexatin®, 10% Topical Solution (Taro Pharmaceuticals, USA, Inc.) in Patients with Mild to Moderate Onychomycosis

Patients will undergo evaluation for clinical and mycological cure of onychomycosis at each of the 7 clinic visits. Randomized patients who withdraw from the study will not be replaced. The study will be conducted according to the following schedule:

Visit Schedule:

- **Visit 1:** Days -35 to -1 (Screening)
- **Visit 2:** Day 1 (Baseline and Randomization / 1st Treatment start)

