9.4.4 Study Blind

The Investigator, staff at the study site, study monitors, and data analysis/management personnel will be blinded to the patient assignment. The patient will be requested not to discuss the appearance of the study product bottle with the Investigator or study staff.

To ensure that information that could potentially bias handling of data is not disclosed, the clinical packaging company will hold the randomization scheme until database lock.

Each bottle will be labeled with a blackout label in order to blind the bottle. Each bottle will be labeled with a two-part, double blind label and will display the following text: "content statement, protocol number, subject number, instructions for use and storage, Sponsor's name, an investigational use statement and warnings: "For Topical Use Only" and "Keep out of reach of children". Part 2 of the label will contain a sealed copy of the randomization scheme (as a scratch off portion of the product label). This label should be detached from the bottle prior to dispensing to the patient and retained in a secure location at the study site, to be opened in case of medical emergency only.

Where possible, the Sponsor and Novum medical monitor should be contacted before breaking the blind for any patient. In the event the blind is broken for any reason Sponsor and Novum should be notified as soon as possible in writing of the details of the occurrence.

At the conclusion of the study, after the database has been locked, each site will be sent the full study randomization scheme that should be retained with the study documents in the event of an FDA Inspection.

The bottles used for all three study products are identical in size, shape and color. A standard label overlay will be used and there is no difference in odor of the products. Therefore, all three products are indistinguishable. This will allow the treatment phase of the study to be conducted under double-blind conditions, such that neither the patient nor the Investigator or study staff members will know the identity of each patient's treatment.

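### A disclosed fixed block of 3, boxed by block, lets one opened treatment code inform on two other patients: probably a small leak, and cheap to close

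*Protocol*

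**What the plan says.** - **Block.** Protocol 9.4.3.2: "The randomization will be generated in blocks of 3, containing the study products in three configurations". SAP section 4 repeats this. Protocol 9.1 gives the ratio: "The randomization scheme will be 1:1:1 (Active Treatment A: Active Treatment B: Placebo C". So each block has exactly one patient per group, and only one configuration has placebo in the first course: "C. bottles #1 & 2 – Placebo and bottles #3 & 4 – Placebo".
- **Box.** Protocol 9.4.3.2: "Three patients worth of study product bottles 1 & 2 will be packed into a larger box", and the text calls that box a block. Protocol 9.4.2 agrees: "One block will consist of three boxes of study product containing 2 bottles (#1 & 2) according to the randomization code".
- **Order.** Protocol 9.4.3.1 says that the numbers "will be assigned in ascending order beginning with the lowest number at each study site", so a patient's two block-mates can be picked out.
- **Codes.** Protocol 9.4.4: "Part 2 of the label will contain a sealed copy of the randomization scheme (as a scratch off portion of the product label". This part is detached before dispensing and stored securely at the site. It is reserved for medical emergencies. The sponsor and medical monitor are to be contacted beforehand where possible, and any break is to be reported in writing.

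Neither document describes varying block sizes or withholds the block size from sites.

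**The concern.** A code break is meant to unblind one patient. Here the staff who open it know that the other two patients in the box make up the rest of an A, B, C set. They can infer something about patients who are still under assessment.

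The same staff produce much of the primary endpoint. The investigator judges nail involvement by eye (Protocol 9.6.13), and the KOH preparation is examined at the site (Protocol 9.5.4, 9.5.7 and Appendix B). The investigator may also drop a patient for lack of efficacy, which makes that patient a clinical failure (Protocol 9.3.5, SAP 8.5). Knowing or suspecting a block-mate's product could influence any of these. The plan removes patients whose returned bottles show unblinding from the ITT population (Protocol 10.3.1), but it has no rule for their block-mates.

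**Working it through.** **Inputs.** Block size 3 (Protocol 9.4.3.2, SAP 4); ratio 1:1:1 (Protocol 9.1); only C has placebo in bottles 1 and 2 (Protocol 9.4.3.2); up to 180 patients (Protocol 10.2). The plan gives no figure for unblinding, so there is none to reproduce. The sample-size calculation does not enter.

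**Before any code is opened.** A block has 3! = 6 equally likely orders. Each patient is on placebo in course 1 with probability 1/3 and on active with probability 2/3.

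**One code opened, showing the group.**

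| Opened code | Probability | Orders left | Each block-mate on placebo in course 1 | Still open |
|---|---|---|---|---|
| C | 1/3 | 2 of 6 | 0 | A versus B, 50/50 |
| A or B | 2/3 | 2 of 6 | 1/2 (was 1/3) | which block-mate is C |

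If the label shows only what is in bottles 1 and 2, Placebo is equivalent to C. Test leaves 4 of 6 orders, with exactly one block-mate on placebo, each with probability 1/2. The placebo probabilities are the same.

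**Average gain for a guesser.** The best guess of a block-mate's course-1 product is right with probability 2/3 before the break. Afterwards it is right with probability 1/3 × 1 + 2/3 × 1/2 = 2/3. The average does not improve; the damage lies in the one third of cases where C is opened.

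**Two codes opened in one box.** If the code shows the regimen, the third patient is always identified. If it shows only bottle content:
- The opened pair is A and B with probability 1/3. Test and Test then leave C.
- Otherwise (2/3) the pair reads Test and Placebo. The third patient is on active in course 1, with A versus B open.

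**Larger blocks.** With known block size b and k = b/3 per arm, another patient in the block is in the opened arm with probability (k − 1)/(b − 1), and in each other arm with probability k/(b − 1).

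| Known block size | Placebo probability after opened C | After opened A or B |
|---|---|---|
| 3 | 0/2 = 0 | 1/2 = 0.50 |
| 6 | 1/5 = 0.20 | 2/5 = 0.40 |
| no block information | 0.333 | 0.333 |

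With a block of 6, one opened code identifies no block-mate's course-1 product with certainty.

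**Scale.** If m codes are opened in different full boxes, 2m other patients are touched, and on average 2m/3 of them are shown to be on active. The documents do not give m. Assuming m from 1 to 5, this is 2/180 = 1.1% to 10/180 = 5.6% of patients touched, of whom on average 0.7 to 3.3 are known to be on active.

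**Price of blocks of 6.** A site that stops part-way through a block of 3 has at most 1 patient's difference between two arms. With a block of 6 (2 per arm) it is at most 2.

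**The case against.** The strongest reply is that nothing leaks unless a code is opened, and Protocol 9.4.4 restricts that to emergencies. Protocol 7.4 reports few adverse events and plasma concentrations below quantitation, so emergencies needing a code should be rare. The products are described as indistinguishable, which answers the more usual worry about small blocks, namely guessing from visible treatment differences. Small blocks also serve the analysis: SAP 8.7 justifies the site-stratified CMH test by balance within site. All of this stands. It limits the size of the effect but does not remove the mechanism.

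Stronger readings are tempting but not supported:
- *That the plan could not detect the problem.* Breaks are reported in writing, so block-mates can be traced once the list is released. Returned bottles are inspected (Protocol 9.5.6, 9.6.9), and culture is read centrally (Protocol 9.6.17). An independent panel reviews the photographs (Protocol 9.6.13), and SAP 8.2.3 repeats the primary endpoint and its sensitivity analyses with that nail evaluation. The protection is partial: that analysis is limited to patients with 10% to 35% involvement on the photographic evaluation, and it still uses the on-site KOH.
- *That two codes always fix the third patient.* This holds only if the code shows the regimen, which Protocol 9.4.4 does not say.
- *That each site holds the whole list.* The phrase about a sealed copy of the scheme could be read so, but the same section leaves the scheme with the packaging company until database lock. The text needs clarifying and does not prove a wider leak.
- *That the readings are biased.* They could be; nothing in the documents shows that they are.

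**Conclusion.** The point holds as an avoidable weakness in concealment, not as an error in the analysis. One opened code shows that both block-mates are on active product in course 1 in one third of cases. In the other two thirds it moves each block-mate's placebo probability from 1/3 to 1/2 without identifying either. The total effect depends on the number of code breaks, which the documents do not predict, and is probably small. The components exposed are the investigator's nail reading and the on-site KOH. Sample size and power are not affected.

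This assumes that staff use the printed block size and that boxes stay intact. Site-to-site transfer of product, which Protocol 9.4.2 allows with sponsor approval, could split a box.

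**What to change.** **Before supplies are made.** Generate the list within site in randomly mixed blocks of 3 and 6. Take the block size out of the text that sites see. Pack kits in numbered runs that do not coincide with blocks. Keep 1:1:1 and ascending assignment. The cost is a new list and packing instruction, and a maximum within-site difference between two arms of 2 patients rather than 1. That essentially keeps the balance the CMH test relies on. Blocks of 3 remain in the mix, but staff could no longer tell which patients share one.

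**If supplies already exist.** Use the reported code breaks to identify block-mates from the list after database lock. Add to SAP 8.2.1 a sensitivity analysis of the primary endpoint that excludes them. It needs no new data. Carry the design change into the Phase 3 studies that this trial is meant to size (Protocol 10.6).

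**In either case.** State in Protocol 9.4.4 whether the scratch-off shows the regimen or only the bottle's content, and that it covers one patient only, if that is what is meant.

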A Randomized, Placebo-Controlled, Double-Blind, Parallel-Group, Multi-Site Phase 2b Clinical Study to Assess the Efficacy, Safety and Tolerability of 8-Week Regimens of Novexatin®, 10% Topical Solution (Taro Pharmaceuticals, USA, Inc.) in Patients with Mild to Moderate Onychomycosis

	
directly involved in the conduct of the clinical study or employed by the clinical site, or a first-degree relative of a site employee.
 
25. Patients with previous exposure to the study drug, or with known allergy to the drug or any of its components.

Route of Administration	Topical
Treatment	
Thin coat of study product will be applied to all toenails on feet with affected toenails once daily for either one or two 8-week intervals over an approximate 11-month intermittent treatment period (at Days 1 – 56 and Days 281 – 336) and 12-month study duration.
 
The product should be applied at approximately the same time every day, preferably in the morning, after the patient has washed all toes with a non-medicated cleanser, rinsed with warm water, and patted dry with soft towel. The nails should be completely dry before applying the study treatment.

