9.5.2 Visit 2: Day 1 (Baseline and Randomization / 1st Treatment start)

1. **Inclusion/Exclusion Criteria:** Patients will be questioned to ensure they continue to meet all inclusion/exclusion criteria for the study. Patients with a negative result for the fungal culture test on Visit 1 will receive appointment cancellations for Visit 2, and will not participate in the study.
2. **Concomitant Medications:** Review and record since Visit 1.
3. **Urine Pregnancy Test:** For women of childbearing potential, a urine pregnancy test will be performed to evaluate pregnancy. Any patient with a positive pregnancy test will not be allowed to participate in the study.
4. Trimming target nail, if needed.
5. **Investigator Clinical Assessment:** Perform a foot/toenail exam. Infected toenail count will be recorded. Nail appearance will be recorded.
6. **Evaluation of Toenail Appearance and Condition:** The investigator and patients will perform a visual assessment and rate target toenail appearance and condition per Appendix A.
7. **Visual Assessment:** The target toenail involvement will be recorded. The toenail (one of the two great toenails) that meets inclusion/exclusion criteria will be identified and designated as the target toenail and used for all further evaluations.
8. **Planimetry Assessment:** Appropriate photographic documentation will be obtained in accordance with Canfield Scientific Inc. guidelines for the planimetry assessment.
9. **Dispense Randomized Study Product and Administration Instructions:** Patients will be randomly assigned to one of the three **treatment groups** of the study, and will receive a randomization number. Qualified patients will be provided with two bottles of randomized study product. A set of instructions to apply the study product at home will be provided, along with supplies including standardized non-medicated bar of soap and towel.
10. **Dispense Patient Diary:** A diary along with instructions to record dose frequency and timing, adverse events and concomitant medications will be provided.
11. **Administer First Dose:** Clinic staff member will observe the first application of study product by the patient in the clinic.

A Randomized, Placebo-Controlled, Double-Blind, Parallel-Group, Multi-Site Phase 2b Clinical Study to Assess the Efficacy, Safety and Tolerability of 8-Week Regimens of Novexatin®, 10% Topical Solution (Taro Pharmaceuticals, USA, Inc.) in Patients with Mild to Moderate Onychomycosis

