**Novexatin 10% topical solution**

**Protocol / Study No. NVXT 1404/71442603**

**4. RANDOMIZATION AND BLINDING**

The study product will be packaged and blinded by an independent clinical packaging company. The randomization will be generated in blocks of 3, containing the study products in three configurations:

- A. bottles #1 & 2 – Test and bottles #3 & 4 – Placebo
- B. bottles #1 & 2 – Test and bottles #3 & 4 – Test
- C. bottles #1 & 2 – Placebo and bottles #3 & 4 – Placebo.

Three patients worth of study product bottles 1 & 2 will be packed into a larger box. This larger box will be designated “one block” of study product. The study product bottles 1 & 2 will be blinded, packaged and delivered to the study site in blocks at the beginning of the enrollment. Bottles 3 & 4 will be delivered to the study site before Visit 5 (2nd treatment start).

At each Visit 2 and Visit 5 each patient will receive two 5 ml bottles of study product according to the randomization code. Patients will be randomized to a treatment regimen in a blinded fashion by assigning randomization numbers in ascending sequential order starting with the lowest available randomization number at each site. All patients randomized will be identified by initials, date of birth, and a unique six-digit patient number. The first two-digits will identify the Investigator site where the patient was enrolled and the last four will correspond with the randomization number of study product bottle assigned to the patient. A perforated or two-part label will be attached to each of the small sized boxes of study product supplies. Both pieces of the label will include the following information: Protocol number, randomization number, space for patient’s initials, statement that the study product is for investigational use only, space for dispensing date and the Sponsor’s name. In addition all patients will be provided with written instructions on how to use the study product. One part of the label shall remain attached to the box. The other part will be removed prior to dispensing and attached to the study product log.

The Investigator, staff at the study site, study monitors, and data analysis/management personnel will be blinded to the patient assignment.

At the end of the study, after all the clinical data has been entered and the study database has been locked, a copy of the randomization will be sent to the statistician.

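### Two 5 ml bottles per 8-week course cannot supply the stated per-nail volume to patients treated on both feet: 16.8 ml is needed and 10 ml is given

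*Protocol*

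**What the plan says.** **Supply.** Protocol section 9.4.3.2 states: "At each Visit 2 and Visit 5 each patient will receive two 5 ml bottles of study product". SAP section 4 repeats it: "each patient will receive two 5 ml bottles of study product according to the randomization code". The Visit 2 and Visit 5 procedures (Protocol sections 9.5.2 and 9.5.5) agree: "Qualified patients will be provided with two bottles of randomized study product". Section 9.6.8 describes dispensing of bottles 1 and 2 at Visit 2 and bottles 3 and 4 at Visit 5, and no other dispensing.

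**Amount per nail.** Protocol section 9.4.1 says that 30 to 50 µl "will cover a single nail and nearby skin, depending on the size of the nail", and that daily application "will provide between 3 - 5 mg of Novexatin per nail". Section 9.4.2 gives the strength: "presented as a 100 mg/ml (10%) solution of net peptide".

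**Nails treated.** Section 9.4.1 tells the patient to "spread a liberal amount of the study product evenly across all toenails on feet with affected toenails". The Synopsis, under Treatment, has the same nails but a different amount: "Thin coat of study product will be applied to all toenails on feet with affected toenails once daily".

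**Doses.** Section 9.4.5 schedules 56 doses per course and requires 42 to 70. One dose means treating each toenail, affected or not. Missing four or more doses in a row also makes a patient non-compliant.

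**Who may enter.** The schematic (section 5.0) and section 9.3 provide for patients with both great toenails infected.

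**The concern.** The volume per nail, the number of nails, the number of doses and the bottle count are stated in different sections, and no section multiplies them out. For a patient treated on both feet they do not fit together.

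A two-foot patient who puts the stated minimum on every nail runs out partway through the course. No visit is scheduled between Day 1 and Day 57, or between Day 281 and Day 337, at which this would be noticed. That patient then fails both compliance rules by following the instructions. Section 9.3.4 lists failure to follow dosing procedures among the possible reasons for early termination.

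A patient who makes the bottles last has a diary that looks compliant, because the diary records the date and time of each dose, while the nails receive less on average than the protocol states. Under-dosing with active product could dilute an effect: in the first course for Groups A and B, and in the second for Group B. Section 10.6 says that the efficacy results will be used to size the Phase 3 studies.

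**Working it through.** **Inputs**

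- Supply per course: 2 × 5 ml = 10 ml = 10,000 µl (Protocol 9.4.3.2; SAP section 4)
- Volume per nail: 30 to 50 µl (Protocol 9.4.1)
- Strength: 100 mg/ml (Protocol 9.4.2)
- Doses per course: 56, range 42 to 70 (Protocol 9.4.5)
- Assumptions: five toenails per foot, 5 ml of usable product in each bottle, no wastage

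**The plan's own figures first.** These all reproduce:

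- 0.030 ml × 100 mg/ml = 3 mg and 0.050 ml × 100 mg/ml = 5 mg, so 30 to 50 µl is a per-nail volume
- 0.75 × 56 = 42 doses and 1.25 × 56 = 70 doses

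The protocol states no total volume per course, so there is no such figure to check.

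**Volume needed** = nails × µl per nail × doses, against 10 ml supplied:

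| Nails | µl per nail | 42 doses | 56 doses | 70 doses |
|---|---|---|---|---|
| 10 | 30 | 12.6 ml | 16.8 ml | 21.0 ml |
| 10 | 50 | 21.0 ml | 28.0 ml | 35.0 ml |
| 5 | 30 | 6.3 ml | 8.4 ml | 10.5 ml |
| 5 | 50 | 10.5 ml | 14.0 ml | 17.5 ml |

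At 30 µl for 56 doses, 10 ml covers 10,000 / (30 × 56) = 5.95 nails. That is enough for one foot and not for two. The two-foot shortfall is 16.8 − 10 = 6.8 ml for the full course and 12.6 − 10 = 2.6 ml for the 42-dose floor.

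**What a two-foot patient can do with 10 ml**

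1. *Exactly 30 µl on every nail.* 10,000 / (10 × 30) = 33.3, so 33 full doses (33/56 = 58.9%). The product runs out on Day 34 of the course, and 56 − 33 = 23 consecutive full doses are missed. Both compliance rules are broken.
2. *Stretched evenly over 56 days.* 10,000 / (10 × 56) = 17.9 µl, or 1.8 mg, per nail on average. Reaching only 42 doses still requires the average to fall to 10,000 / (10 × 42) = 23.8 µl.
3. *Both great toenails kept at 30 µl.* (10,000 − 2 × 30 × 56) / (8 × 56) = 6,640 / 448 = 14.8 µl, or 1.5 mg, for each of the other eight nails.

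**One-foot patients.** 10,000 / (5 × 56) = 35.7 µl per nail on average. This covers the lower end of the range but not 50 µl on every nail.

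**The case against.** **30 µl is descriptive, not metered.** Section 9.4.1 calls it approximate, the brush holds up to 50 µl, and the patient is given a qualitative instruction. A patient who paints all ten nails thinly for 56 days meets both compliance rules whatever the volume. This stands as far as it goes: non-compliance follows only in the first scenario. But a course stretched in this way delivers less per nail than section 9.4.1 states.

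**Small toenails need less.** The documents give no volumes by nail size, so 30 µl on all ten nails is an assumption. However, the stated range already varies with nail size and 30 µl is its lower end. The 56-day average of 17.9 µl is about 60% of that.

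**30 µl might mean the whole application.** One sentence in section 9.4.1 puts a single dose at about 30 µl, which read alone would need only 30 × 56 = 1.68 ml per course. The sentences that follow, giving volume and milligrams per nail, rule this out.

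**Extra supply is not forbidden.** The plan allows unscheduled visits and sponsor-approved shipping between sites, and requires reconciliation records. None of these sets a resupply rule for a patient.

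**The effect on the results is limited.** This stands. Supply is the same in all arms. The 42-dose floor defines no analysis population (Protocol 10.3; SAP section 7). Every efficacy endpoint concerns one great toenail, which could still receive 30 µl for 56 days if the other nails were rationed. No instruction tells the patient to ration, though, and section 9.4.1 asks for an even spread.

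**Conclusion.** The concern holds and should be fixed. Followed as written, the plan cannot deliver its own lowest stated volume to a patient treated on both feet: the 10 ml supplied is 10/16.8 = 60% of what 56 doses require, and it falls short of the 42-dose floor as well. The calculation is conservative, since it takes the bottom of the range and allows no wastage.

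Confidence is high for the shortfall and lower for its consequences. The documents do not give the share of two-foot patients, so neither the number affected nor any effect on cure rates can be worked out. Under-dosing of the target nail is possible but does not necessarily follow. The conclusion does not extend to one-foot patients at 30 µl per nail, for whom the supply is adequate.

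**What to change.** Dispense at least four 5 ml bottles per course to patients treated on both feet, under the same randomization number, or put four in every kit in all three groups. Since 16.8 / 5 = 3.36, four is the smallest whole number that works. Three bottles average 15,000 / 560 = 26.8 µl per nail; four average 20,000 / 560 = 35.7 µl, the same as one-foot patients get now. Four also cover a one-foot patient at 50 µl on every nail (14 ml).

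Four bottles meet the stated minimum for the 56 scheduled doses and no more. They do not cover ten nails at 50 µl (28 ml), or the permitted maximum of 70 doses at 30 µl (21 ml).

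Update the bottle counts and numbering in Protocol sections 9.4.2, 9.4.3.2, 9.5.2, 9.5.5 and 9.6.8 and in SAP section 4. Use one instruction on the amount to apply in the Synopsis and section 9.4.1.

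**Cost.** Extra product, and repackaging and relabelling of kits that are packed in blocks of three and tied to randomization numbers. This is four more bottles per two-foot patient over both courses, or at most 180 × 2 courses × 2 = 720 if every kit is enlarged. Protocol and SAP wording changes; the sample size and analyses do not.
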